# Project title: Reducing postoperative bleeding after hysterectomy via independent closure of vaginal cuff angles

Principal Investigator: [name] MD FACOG

Study Coordinator/ Study Contact: [name], [name]

Participating Clinician: [name] MD, [name], [name]

Affiliations: Texas Tech University Health Science Center El Paso, Paul L. Foster School of Medicine

Hysterectomy is the most common surgical procedure in the United States, with over 600,000 performed annually. There has been a dramatic improvement in expected postoperative course secondary to the advancement of minimally invasive gynecologic surgery. With the advent of laparoscopy and robotic surgery, even the most complex cases can be successfully performed via a minimally invasive approach. What used to be a major surgery that required a prolonged inpatient stay has become an outpatient procedure where patients are discharged home a few hours after the operation. Although the recovery period is shorter than in the past, there are still some postoperative complaints that are relatively common, and can impair quality of life. One of them is postoperative vaginal bleeding. Although this can be a sign of a more serious problem such as vaginal cuff dehiscence, the grand majority of times it is related to granulation tissue in the vaginal cuff that although may be self-limiting, can be bothersome and concerning to patients. Not only does this bleeding impair quality of life, but it's one of the most common reasons for emergency room visits after surgery. Multiple studies have shown that postoperative vaginal bleeding and return to the hospital significantly affect patient satisfaction.

Anecdotally, bleeding originates from granulation tissue at the angles of the closure, although there hasn't been any studies specifically investigating this. A common approach to laparoscopic cuff closure involves a running barbed suture, with or without separate closure of the lateral angles. Recently, laparoscopic closure of the vaginal cuff was found to be superior when compared to vaginal closure in terms of vaginal cuff dehiscence. This RCT also evaluated vaginal cuff bleeding as a secondary outcome, but this was recorded as he presence of bleeding at 3 months after surgery. The closure technique in this study was a running non-barbed suture, without independent suturing of the angles. Although a running suture placed laparoscopically may provide adequate tensile strength throughout the cuff to promote healing, the tension at the corners may be less than at the center when using barbed suture, hence potentially increasing the risk of bleeding. Furthermore, the second angle may be more difficult to access when the remainder of the cuff is re-approximated.

We propose prospectively evaluating if adding separate sutures to the angles of the vaginal cuff before running barbed suture reduces the incidence of patient's perception of bleeding after surgery.

## **Primary Objectives:**

Determine if closing angles of vaginal cuff separately during laparoscopic hysterectomy decreases incidence of vaginal bleeding after surgery.

#### Secondary objectives:

Determine if there is a difference in patient satisfaction after surgery by comparing results from SF-36 questionnaire

Determine if this technique changes the rate of vaginal cuff complications (cellulitis, dehiscence, vaginal cuff hematoma, and abscess)

Evaluate the difference in operative time between techniques for this portion of the procedure.

## Hypothesis

Performing a separate closure of the vaginal cuff angles after hysterectomy will decrease incidence of postoperative bleeding

# **Inclusion Criteria-**

• Pre-menopausal patients scheduled to undergo hysterectomy via laparoscopic/robotic approach for benign indications (Ages 18-60, who have had at least one menstrual cycle in the last year).

# **Exclusion Criteria-**

- Patient's that incur in an intraoperative bowel or urologic injury during the hysterectomy that requires repair. If injury occurs after randomization (during vaginal cuff closure), this will be recorded and reviewed by the study's safety officer
- Patients scheduled to undergo a concomitant vaginal procedure (Mid-urethral sling, anterior/posterior repair)
- Patients scheduled to undergo pelvic floor repair (utero-sacral ligament suspension)
- Patients with known preoperative malignancy
- Patients in which a total hysterectomy is not completed

## Sample Size

Sample size was calculated for primary outcome. Based on our experience when angles are not secured separately, incidence of at least mild spotting ranges around 20%. We expect the intervention to decrease this to an incidence of 5%, In order to detect the expected change with a significance level of 5% and a power of 80%, a sample of 154 patients is required (77 per group) using Kelsey's formula.

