Between 90-114 days after surgery, patients will be called by a member of the research team and given a survey regarding bleeding and quality of life (See ANNEX 3 and SF-36 survey).

A retrospective chart review will also be performed 3 months after enrollment to evaluate for any postoperative visits to the emergency department / re-admissions / re-operations / infections.

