# Data Handling

A master key will be generated during randomization. It will contain patient initials and medical record number, and a unique code. Only the primary investigator will have access to this master key which will be kept in an encrypted secure computer at Texas Tech.

A separate de-identified secure database (Redcap) using the unique code as index will be used for collection of data points. The baseline demographic data will transferred directly into the deidentified database after randomization. All collection forms /surveys will be destroyed after data is transferred into electronic database. Using the master key, we will perform a retrospective chart review to complete final data points (pathology results, return to ER, re-admissions, re-operations). All data analysis will be carried out in SPSS version 24 (IBM, Armonk, NY, USA). Continuous baseline demographic variables: (age, BMI, operating time and uterine weight) will be compared using t-student, and Chi square for categorical variables (steroid use, diabetes). Postoperative bleeding will first be evaluated as a binary categorical value, and compared using Chi Square. Inter-quartile ranges/t-student and logistic regression will be utilized to compare SF-36 results at 3 months. We will also use Chi Square to compare categorical values such as return to ER, Infection and re-admission.

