0 1 2 3 4 5 6 7 8 9 10

In the 6 months before surgery, do you consider yourself sexually active?

Yes No

Have you experienced vaginal bleeding/spotting after your surgery (not counting first 2 days after surgery)?

 Yes
 No

 If yes, with what frequency?

 Daily
 Most days
 Infrequent

 How would you best dascribe the bleeding?

 Only when using restroom
 Spotting throughout day
 More than spotting

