#### Spanish version:

En una escala del 0-10, con 0 siendo nada de dolor, y 10 siendo el peor dolor posible, ¿Qué número representaría su dolor pélvico/vaginal en este momento?

0 1 2 3 4 5 6 7 8 9 10

En los 6 meses antes de su cirugía, se considera sexualmente activa?

Si No

¿Ha tenido sangrado vaginal o manchado después de su cirugía? (Sin contar los primeros dos días después de la operación)

Si	No									
	Si la respue	sta fue sí, ¿con q	ue frecuencia	?						
	Diario	La mayoría d	e los días	Infrecuente						
	¿Cómo des	¿Cómo describiría su sangrado?								
	Solo al ir al baño		Manchado	durante el día	Más que manchado					

# ANNEX 3

English Version										
Have you experienced vaginal bleeding in the last 2 weeks?										
Yes		No								
Have you had vaginal intercourse since your surgery?										
Yes		No								
If yes, rate from 0-10 how painful the last time you had intercourse was? With 0 being no pain and 10 being the worst pain ever										
0	1	2	3	4	5	6	7	8	9	10
Have you been to the emergency department after your surgery for any related surgical problems?										
Yes		No								
Spanisł	n Versior	ı								
¿Ha tenido sangrado vaginal en las últimas 2 semanas?										
Si		No								
¿Ha tenido relaciones sexuales vía vaginal desde su cirugía?										
Si		No								
Si la respuesta fue sí, en una escala del 0 al 10, con 0 siendo nada de dolor y 10 siendo el peor dolor posible, ¿Cuánto dolor tuvo durante la última vez que tuvo relaciones sexuales?										
0	1	2	3	4	5	6	7	8	9	10
¿Ha tenido que visitar el departamento de urgencias desde su cirugía, por problemas relacionados a la operación?										

Si No

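### The 3-month bleeding question (Annex 3) does not name spotting, the event the trial is sized on, and the protocol does not say that the Annex 2 answer is the single primary outcome

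*Protocol*

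**What the plan says.** The Primary Objectives section asks whether separate closure of the cuff angles "decreases incidence of vaginal bleeding after surgery". The Sample Size section is more specific about the event: "Based on our experience when angles are not secured separately, incidence of at least mild spotting ranges around 20"%, with 5% expected under the intervention and 154 patients (77 per group) required. The analysis text in Data Handling returns to the general term: "Postoperative bleeding will first be evaluated as a binary categorical value, and compared using Chi Square". None of the three names a survey, a time window or the answer that counts as an event.

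Bleeding is asked about twice.

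- **Annex 2**, handed out at the visit 10-20 days after surgery: "Have you experienced vaginal bleeding/spotting after your surgery (not counting first 2 days after surgery". The Spanish form also names spotting: "Ha tenido sangrado vaginal o manchado después de su cirugía". A Yes leads to items on frequency and amount.
- **Annex 3**, by telephone 90-114 days after surgery: "Have you experienced vaginal bleeding in the last 2 weeks". In Spanish: "Ha tenido sangrado vaginal en las últimas 2 semanas". Neither version mentions spotting, and neither has graded follow-on items for bleeding. Methods describes patients at this contact as being "given a survey regarding bleeding and quality of life".

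**The concern.** A trial sized on spotting should ask about spotting wherever it measures its main event. At 3 months the form does not. A woman who has only spotting may not regard it as vaginal bleeding and may answer No, although the same symptom would count as Yes under Annex 2. A change in the proportion of Yes answers between the two contacts would then mix a real change in symptoms with a change in the question.

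The second part is that the document does not link its primary outcome to a question. If this stays open until data are seen, either survey's answer could be reported as the incidence of postoperative bleeding, and a reader could not tell which window the 20% and 5% describe.

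The two parts differ in how easily they can be repaired. An analysis plan can name the primary outcome. It cannot recover answers to a question that was not put, because the Annex 3 wording is fixed in the form.

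**Working it through.** **Step 1: reproduce the plan's figure.** Inputs from the Sample Size section: p1 = 0.20, p2 = 0.05, significance level 5%, power 80%. Methods gives 1:1 allocation. The number of sides is not stated; two-sided is assumed and reproduces the stated total.

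Kelsey's formula with equal groups: n per group = (z_α/2 + z_β)² × p̄(1 − p̄) × 2 / (p1 − p2)²

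- p̄ = (0.20 + 0.05)/2 = 0.125, so p̄(1 − p̄) = 0.125 × 0.875 = 0.109375
- (1.96 + 0.8416)² = 7.849
- n = 7.849 × 0.109375 × 2 / 0.15² = 1.717 / 0.0225 = 76.3, rounded up to 77 per group, 154 in total

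The stated figure is reproduced. The open question is which recorded answer the 20% and 5% belong to.

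**Step 2: set the two questions beside the planning event.**

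| | Planning event (Sample Size) | Annex 2 | Annex 3 |
|---|---|---|---|
| Time of asking | not stated | day 10-20 | day 90-114 |
| Window | not stated | after day 2 up to the visit | the 14 days before the call |
| Spotting named, English | yes | yes | no |
| Spotting named, Spanish | – | yes | no |
| Graded follow-on items | – | frequency and amount | none |
| Threshold | mild spotting or more | Yes/No | Yes/No |

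The Annex 3 window opens between day 90 − 14 = 76 and day 114 − 14 = 100, so it never overlaps the Annex 2 window, which closes by day 20. The two items therefore differ both in the event named and in the period covered. *Mild* is not an answer option in either annex, so the mapping from the planning event to a Yes is itself unstated.

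**Step 3: which question is the likely primary?**

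- Only Annex 2 names spotting, as the planning event does.
- Data Handling says bleeding will *first* be treated as binary, which implies a later graded look. Only Annex 2 collects grades.
- Data Handling attaches the 3-month time point to the SF-36, not to bleeding.
- The introductory background contrasts this trial with an earlier randomised trial of cuff closure that recorded bleeding at 3 months.
- Time frame describes the 3-month contact as a satisfaction survey.

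All five point to Annex 2. On the other side, Methods describes the call as partly about bleeding, which shows only that bleeding is asked about again. Annex 2 is the reasonable inference, but the protocol does not state it.

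**Step 4: what follows for Annex 3.** If Annex 2 is primary, the Annex 3 wording changes neither the primary result nor its power. What it affects is the 3-month bleeding answer, which does not expressly ask about the event the trial is built on.

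**The case against.** The strongest reply is that the intent is clear enough. The indications in Step 3 all favour Annex 2, so naming it is one sentence of clarification that an analysis plan may already contain. Bleeding at 3 months is not among the listed secondary objectives, and a two-week look-back is a legitimate measure of bleeding still present at that time. Annex 3 does not exclude spotting either: a woman who is spotting may well answer Yes.

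Most of this stands. The look-back needs no change, and the ambiguity about the primary is modest. What does not fall away is the wording. The protocol itself presents the call as a bleeding survey, the item leaves out in both languages a word that Annex 2 includes in both, and no analysis plan can repair that afterwards.

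A reader might infer more than the document supports:

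- *That the primary cannot be determined.* The indications above make Annex 2 the likely choice.
- *That spotting is not captured at all at 3 months.* The item does not name it; some women with spotting may still report it.
- *That the weeks between the two windows are a flaw.* The protocol nowhere promises continuous recording of bleeding up to the call.
- *That the trial is underpowered.* Nothing in the document suggests that the 20% belongs to another window, and the calculation is correct as stated.

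**Conclusion.** The point holds in a limited form and is worth fixing. The Annex 3 item does not expressly ask about the event on which the trial is sized, so its answers are not comparable with Annex 2 or with the planning event. The protocol also leaves the primary outcome without a named survey, window or threshold, although Annex 2 is the likely one.

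The size of the effect on the 3-month answers cannot be given, because the protocol reports no bleeding rate for either survey and no share of women with spotting alone. Both arms get the same question, so no bias between arms is shown; the issue is which event is recorded. The sample size of 154 stands, provided the sponsor confirms that 20% versus 5% refers to a Yes on Annex 2. The assumptions are the two-sided test and the reading of Annex 2 as primary.

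**What to change.** 1. In Annex 3, add *or spotting* to the English two-week item and *o manchado* to the Spanish one. Keep the two-week look-back as a measure of bleeding still present at 3 months.
2. In the objective, Sample Size and Data Handling text, state that the single primary outcome is the Annex 2 yes/no answer at the day 10-20 visit, covering the time since surgery without the first two days, and that Annex 3 bleeding is secondary. Do this before outcome data are seen.
3. Have the sponsor confirm that any Yes is what the mild-spotting threshold means, and that 20% versus 5% refers to that question and window. If so, the total stays at 154. If not, the planning rates must be restated for that window and the total recomputed.

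The cost is a few words on an existing form, one sentence in three places and one confirmation, with no added visits or questions and, if the rates are confirmed, no added patients. The downside is that 3-month answers collected before the change would not be directly comparable with later ones, so the form version should be recorded for each call.

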## Methods

Participants will be enrolled based on eligibility criteria. They will be consented to participate in the office during their preoperative visit. Baseline demographic data collected will include Age, BMI, Diabetes status, HgbA1c within the last 3 months if available, and daily steroid use. Subjects will be allocated on a 1:1 ratio via block randomization in blocks of 4. Assignment will be performed after completion of hysterectomy, before cuff closure, via a pre-generated sequential masked randomized

list. An opaque sealed envelope containing group allocation will be opened by the circulating nurse prior to vaginal cuff closure, who will communicate contents to the surgeon.

Vaginal cuff-closure will be performed by high-volume surgeons with subspecialty training in minimally invasive gynecology who have similar operating techniques. If the subject's group corresponds to "Control group", the surgeon will re-approximate the cuff in a standard fashion, using a running-barbed suture (2-0 V-LOC 90 with tapered needle), starting at the right apex, moving towards the left, and then back-tracking once to further reinforce the closure. If the allocation corresponds to "Apical stitches", surgeon will use 0 polyglactin 910 suture on a tapered needle to place figure of 8 sutures on both (left and right) apexes. Knot tying technique (intra-corporeal vs extracorporeal) will be up to surgeon preference. After this is completed, barbed suture will be used to re-approximate the remainder of the vaginal cuff from right to left, backtracking once at the end for reinforcement. Time when vaginal cuff closure starts and ends will be noted. Surgeon will also examine vaginal introitus at the end of the case, noting any lacerations.

After the surgery, a survey will be filled out by the primary surgeon (See ANNEX 1).

Immediate postoperative care and discharge criteria will be performed per unit guidelines. All patients are instructed to abstain from heavy lifting (more than 30 lbs) and vaginal penetrative sex for 6 weeks.

When patients arrive for their postoperative visit (10-20 days after surgery), a member of the research team who is blinded to allocation will give out a short survey before the patient meets the physician (SEE ANNEX 2). Remainder of visit will occur in a routine fashion.

Between 90-114 days after surgery, patients will be called by a member of the research team and given a survey regarding bleeding and quality of life (See ANNEX 3 and SF-36 survey).

A retrospective chart review will also be performed 3 months after enrollment to evaluate for any postoperative visits to the emergency department / re-admissions / re-operations / infections.

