## Limitations

The main confounding factors when comparing surgical techniques are difference in operating style between surgeons and baseline surgical characteristics (large uteri that may require more dissection and tissue manipulation, etc.). To control for this we are only recruiting patients from 3 surgeons who have a similar operating technique. In addition to this, we are documenting operating time and specimen weight, which can be used to compare both groups and assure that they are homogenous to these potential confounders. Baseline patient characteristics that can influence postoperative healing, such as diabetes and steroid use will also be accounted for. Post-hoc analysis will also be made specifically stratifying the data based on these characteristics.

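### A fixed block size of 4, printed in the protocol of a three-surgeon trial, lets up to a third of allocations be deduced before the envelope is opened if earlier allocations are shared (about 4% from a surgeon's own cases alone)

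*Protocol*

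**What the plan says.** The Methods section fixes both the ratio and the block size: "Subjects will be allocated on a 1:1 ratio via block randomization in blocks of 4". It mentions neither varying block sizes nor stratification.

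On timing, the same section refers to a list drawn up in advance: "Assignment will be performed after completion of hysterectomy, before cuff closure, via a pre-generated sequential masked randomized". For concealment it says "An opaque sealed envelope containing group allocation will be opened by the circulating nurse prior to vaginal cuff closure". The nurse is then described as the person "who will communicate contents to the surgeon". Consent comes earlier: "They will be consented to participate in the office during their preoperative visit".

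The Limitations section adds: "we are only recruiting patients from 3 surgeons who have a similar operating technique". Two of the exclusion criteria can be settled only in theatre: "Patient's that incur in an intraoperative bowel or urologic injury during the hysterectomy that requires repair" and "Patients in which a total hysterectomy is not completed". For an injury during the hysterectomy, and for an uncompleted hysterectomy, that is before the envelope is opened.

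The protocol does not say that surgeons see the list or share results with one another. Nor does it say that the block size is withheld from them.

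**The concern.** An opaque envelope opened late hides only what cannot be worked out beforehand. In a block of 4 with two patients per arm, the remaining allocations are fixed as soon as one arm has used both of its slots. The block size is in the investigators' own document, and each operating surgeon learns the arm of every patient they close. Part of the sequence is therefore open to deduction.

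Three things could be affected before the envelope is opened: how the hysterectomy is carried out, the order in which consented patients are operated on, and how the two in-theatre exclusions are applied. Knowledge of the coming arm, even if not used deliberately, could influence any of them. A later analysis plan cannot repair this once the list and envelopes are in use.

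**Working it through.** **Inputs.** From the protocol: 1:1 allocation in blocks of 4, three surgeons, and 154 patients (77 per group). Assumed, because the protocol is silent: the observer knows the block size and the current position in the block, and knows each earlier allocation in the block with probability *s*.

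**The plan's own figure.** The protocol gives no figure for predictability. Its sample size, used here only as the denominator, reproduces. Kelsey's formula with 20% v 5%, two-sided 5% (sidedness assumed) and 80% power gives 7.849 × 0.125 × 0.875 × 2 / 0.15² = 76.3, so 77 per group and 154 in total.

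**Observer who knows every earlier allocation (*s* = 1).** The six balanced sequences of a block of 4 are equally likely.

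| Position | Probability that the allocation is certain | Best-guess accuracy |
|---|---|---|
| 1 | 0 | 1/2 |
| 2 | 0 | 2/3 |
| 3 | 1/3 (first two in the same arm) | 2/3 |
| 4 | 1 | 1 |

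- Mean certain: (0 + 0 + 1/3 + 1)/4 = 1/3.
- Mean best guess: (1/2 + 2/3 + 2/3 + 1)/4 = 70.8%.
- 154 patients make 38 full blocks plus 2, so 38 × 4/3 = 50.7, or about 51 certain allocations (32.9%).

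**Observer with partial knowledge.** Certainty needs two earlier patients in the block who are both known and both in the same arm.

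- Position 3: *s*² × 1/3.
- Position 4: *s*³ + 3*s*²(1 − *s*) × 1/3 = *s*².
- Mean over the block: (*s*²/3 + *s*²)/4 = *s*²/3.

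| Earlier allocations known | Certain | Of 154 (38 × 4*s*²/3) | Best guess |
|---|---|---|---|
| All (*s* = 1) | 33.3% | about 51 | 70.8% |
| Half (*s* = 1/2) | 1/12 = 8.3% | about 13 | 59.9% |
| Own cases only (*s* = 1/3) | 1/27 = 3.7% | about 6 | 56.9% |

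**Varying block sizes.** Simulation of 400 lists of 154, with an observer who knows all earlier allocations and the set of possible sizes but not the order in which the sizes occur:

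| Scheme | Certain | Best guess |
|---|---|---|
| Fixed 4 (check on the exact result) | 33.0% | 70.6% |
| Random 4 and 6 | 5.5% | 69.2% |
| Random 4, 6 and 8 | 2.4% | 67.9% |

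Making the fixed block larger helps less: a fixed block of 6 still leaves 25% certain for the same observer.

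**The case against.** The strongest case against acting has four parts.

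- **Nothing shows that surgeons can track the sequence.** The list is described as masked, and the nurse reports only the current case. A reader might infer that the surgeons see the list, or that a third of allocations are in fact known in advance. The protocol supports neither reading. One third is an upper bound that requires complete pooling of results. This stands, and the range of 3.7% to 33% is the fair statement.
- **A single list across three surgeons lowers predictability from own cases.** This also stands. The absence of stratification by surgeon is not part of the problem. With fixed blocks of 4 within surgeon, each surgeon would know every earlier allocation in the current block, which is the 33% situation.
- **The routes to bias are thin.** Consent precedes surgery, so choosing whom to enrol is largely closed off. The two in-theatre exclusions are concrete events with limited room for discretion. The surgeon knows the arm throughout the closure whatever the block size. The survey at the postoperative visit is handed out by a blinded team member. All of this stands and lowers the severity, but it does not bring the routes to nil.
- **The remedy removes certainty, not guessing.** For the fully informed observer, best-guess accuracy falls only from 71% to about 68–69%. This stands as well.

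What survives is that three surgeons may easily compare cases, theatre staff may attend more than one surgeon's operations, and nothing in the protocol prevents sharing. No feature of the described design needs a fixed, disclosed block of 4.

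**Conclusion.** The point holds in limited form. The stated scheme makes between about 4% (own cases only) and 33% (all earlier allocations shared) of assignments deducible before the envelope is opened, with about 8% if half are known. These figures assume that the observer knows the block position. The 4% figure also assumes that each surgeon does a third of the cases, independently of position in the block. How much sharing would occur cannot be read from the protocol.

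A reader might go on to infer an inflated type I error or a biased treatment effect of some stated size. The documents do not support that: they give no figure for how far foreknowledge would move bleeding risk, and any number would rest on an invented shift. The sample size is unaffected. This is a cheap improvement to concealment, of low to moderate severity.

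**What to change.** In the Methods section, replace the fixed block of 4 with randomly permuted blocks of varying size (for example 4, 6 and 8). Keep the sizes out of the investigator-facing protocol, known only to the person who generates the list.

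The cost is one changed sentence and a regenerated list with new envelopes. If recruitment stops part-way through a block, the final imbalance could reach 4 (half of a block of 8) instead of 2 (half of a block of 4). With 77 planned per group, that has a negligible effect on power. The gain is the removal of most certain allocations, from 33% to about 2% with sizes 4, 6 and 8, or about 5% with sizes 4 and 6, for a fully informed observer. It should not be presented as making the sequence unguessable.
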